7.14.1 SPONSOR RESPONSIBILITIES

- Determine whether the safety information meets the requirements for expedited reporting to the applicable regulatory authorities
- Prepare and submit the safety report to the applicable regulatory authorities
- Send all participating PIs a safety report and Investigator Safety Letter (i.e., Dear Investigator Letter) that will include a statement if there is or is not any significant new safety information that might influence the risk-benefit assessment of the IP and/or study device, sufficient to consider changes in product administration or overall conduct of the clinical investigation

7.14.2 PRINCIPAL INVESTIGATOR (PI) RESPONSIBILITIES

- Forward a copy of the safety report and Investigator Safety Letter (i.e., Dear Investigator Letter) to their IRB/REB/EC as soon as practical in accordance with the governing policy and/or procedures
- Notify their IRB/REB/EC of safety information (i.e., SAEs, pregnancies, and AESIs) that occur at their clinical trial site in accordance with their local institutional policy

7.15 **POST-TRIAL REPORTING REQUIREMENTS**

PIs are not obligated to actively seek AEs or SAEs beyond the clinical trial reporting period. However, if the PI becomes aware of an AE or SAE that occurs after the Completion or Termination Visit and the event is deemed by the PI to be related to the clinical trial treatment, the PI should promptly document and report the event to the Sponsor.

7.16 CLINICAL TRIAL DISCONTINUATION

INOVIO reserves the right to discontinue the clinical trial at a site or at multiple sites for safety or administrative reasons at any time. In particular, a clinical trial site that does not recruit at a reasonable rate may be discontinued. Additionally, the clinical trial may be discontinued at any time by an IRB/REB/EC, INOVIO, or a regulatory authority as part of their duties to ensure that clinical trial subjects are protected.

If the clinical trial is discontinued and/or the clinical trial site closed for any reason, all IP and devices must be returned to INOVIO or its representative. The PI should ensure that their site file documents are complete prior to archiving, and provide copies of any requested documents to INOVIO for its Trial Master File (TMF).

8.0 **STATISTICAL CONSIDERATIONS**

8.1 STATISTICAL AND ANALYTICAL PLAN

The formal Statistical Analysis Plan is contained in the sections that follow.

8.2 **GENERAL CONSIDERATIONS**

The statistical analysis of the data will be performed by Inovio Pharmaceuticals or its representative.

This is a two-arm, multi-center, placebo-controlled, blinded, and randomized clinical trial in subjects at high risk of SARS-CoV-2 exposure. The study's primary endpoint is the incidence of virologically-confirmed COVID-19 disease starting 14 days after completion of the 2-dose regimen until 12 months post-dose 2. The primary hypothesis is that INO-4800 will be efficacious relative to placebo (relative efficacy > 30%). Secondary efficacy analyses involve non-severe cases, severe cases, cases resulting in death, infection, and timing of symptom resolution. Other secondary analyses concern safety and binding antibody response. Exploratory analyses concern cellular immunological measures.

8.3 **STATISTICAL HYPOTHESES**

The primary hypothesis of relative efficacy greater than 30% will be tested with H₀: $p \ge .70/(.70+k) vs$. H₁: p < .70/(.70+k), where p is the true proportion of subjects with disease who receive INO-4800 relative to the total number of subjects with disease, and k is the total amount of follow-up time in the placebo group divided by the total amount of follow-up time in the INO-4800 group. There are no other formal hypotheses.

8.4 ANALYTICAL POPULATIONS

Analysis populations will be:

The per-protocol (PP) population includes all subjects who receive all doses of Study Treatments and have no protocol violations. Subjects with disease occurring prior to 14 days post-dose 2 will be excluded from the PP population. Subjects in the PP population will be grouped to treatment arms as randomized. Subjects excluded from the PP population will be identified and documented prior to unblinding of the trial database. Analyses on the PP population will be primary for the analysis of efficacy in this trial.

The modified intention to treat (mITT) population includes all subjects who receive at least one dose of Study Treatment. Subjects in this population will be grouped to treatment arms as randomized. Analysis of the mITT population will be considered supportive for the corresponding PP population for the analysis of efficacy.

The intention to treat (ITT) population includes all subjects who are randomized. Subjects in this sample will be grouped to treatment arms as randomized. Analysis of the ITT population will be considered supportive for the corresponding PP population for the analysis of efficacy.

The safety analysis population includes all subjects who receive at least one dose of Study Treatment. Subjects will be analyzed according to the treatments received.

8.5 **DESCRIPTION OF STATISTICAL METHODS**

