8.4 ANALYTICAL POPULATIONS

Analysis populations will be:

The per-protocol (PP) population includes all baseline seronegative subjects who receive all doses of Study Treatments and have no protocol violations. Subjects with disease occurring prior to 14 days post-dose 2 will be excluded from the PP population. Subjects in the PP population will be grouped to treatment arms as randomized. Subjects excluded from the PP population will be identified and documented prior to unblinding of the trial database. Analyses on the PP population will be primary for the analysis of efficacy in this trial.

The modified intention to treat (mITT) population includes all baseline seronegative subjects who receive at least one dose of Study Treatment. Subjects in this population will be grouped to treatment arms as randomized. Analysis of the mITT population will be considered supportive for the corresponding PP population for the analysis of efficacy.

The intention to treat (ITT) population includes all baseline seronegative subjects who are randomized. Subjects in this sample will be grouped to treatment arms as randomized. Analysis of the ITT population will be considered supportive for the corresponding PP population for the analysis of efficacy.

The safety analysis population includes all subjects who receive at least one dose of Study Treatment. Subjects will be analyzed according to the treatments received.

8.5 **DESCRIPTION OF STATISTICAL METHODS**

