3.0 CLINICAL TRIAL DESIGN AND ENDPOINTS

This is a Phase 3, randomized, placebo-controlled, multi-center trial to evaluate the safety, immunogenicity, and efficacy of INO-4800 (1.0mg), administered by intradermal (ID) injection followed immediately by electroporation (EP) using CELLECTRA® 2000 device using a 2-dose regimen (Days 0 and 28) in adults who are at high risk of SARS-CoV-2 exposure. The primary objective of this trial is to evaluate the efficacy of INO-4800 in seronegative subjects.

INO-4800	COVID19-311
Inovio Pharmaceuticals, Inc.	Clinical Protocol

Approximately 6178 seronegative subjects 18 years of age or older are expected to be enrolled and will be randomized at a 1:1 ratio to receive either investigational product (1.0mg INO-4800) or placebo (SSC-0001). See Table 1. Enrollment at the start of the trial will be initiated in subjects 18-50 years of age. Following confirmation that the COVID19-001 Phase 1 trial's safety and immunogenicity data is acceptable in subjects older than 50 years of age, the trial will expand enrollment to include subjects older than 50 years of age. A minimum of 15% of the total sample size of subjects will be 51-64 years of age, and a minimum of 5% of the total sample size of subjects will be 65 years of age and older.

The trial is case-driven. Among the 6178 subjects, a total of 160 observed cases will be required for 90% power to declare the vaccine efficacious (>30%), assuming a true efficacy of 60%. A sample size of 6178 seronegative subjects is expected to be required to achieve the 160 cases assuming an underlying attack rate of 3.7%. The sample size may be increased if the underlying attack rate is lower than projected.

The primary efficacy endpoint window will begin 14 days post-dose 2 and will end at 12-months post-dose 2.

All subjects, investigating site staff (excluding site pharmacy staff) and the Sponsor will be blinded throughout the trial. A group-level unblinding will occur when all subjects' data is complete for the primary efficacy timeframe.

A Data Safety Monitoring Board (DSMB) will convene regularly throughout the trial to review unblinded safety data. An independent, blinded EAC will review and confirm COVID-19 cases. Details of each committee's scope will be provided in charters.

3.1 **PRIMARY OBJECTIVES**

See Table 3.

3.2 **PRIMARY ENDPOINTS**

Table 3: Primary Objective and Associated Endpoints

Primary Objective Associated Primary Endpoint		Associated Primary Endpoint

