3.7 EFFICACY ASSESSMENT

Subjects will receive either investigational product (1.0mg INO-4800) or placebo (SSC-0001) in a 2-dose regimen administered on Days 0 and 28 intradermally followed immediately by EP. Subjects will be monitored through regularly scheduled clinic visits and phone calls throughout the trial. Subjects will be regularly tested for SARS-CoV-2 infection using serologic testing. If COVID-19 disease is suspected based on symptoms or laboratory testing, site personnel will arrange for a clinic visit. Subjects with symptom(s) or a positive virologic test result will be reviewed by the independent blinded EAC. The mechanism for review and confirmation of cases will be outlined in an EAC Charter.

INO-4800	COVID19-311
Inovio Pharmaceuticals, Inc.	Clinical Protocol

3.7.1 CASE DEFINITION FOR VIROLOGICALLY-CONFIRMED COVID-19 DISEASE:

• Positive testing by RT-PCR assay (any source) with any of the following COVID-19 related symptoms:

- Fever or chills
 - Cough
 - Shortness of breath or difficulty breathing
 - Fatigue
 - Muscle or body aches
- Headache
- New loss of taste or smell
- Sore throat
- Congestion or runny nose
- Nausea or vomiting
- Diarrhea

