3.7.2 CASE DEFINITION FOR VIROLOGICALLY-CONFIRMED SARS-COV-2 INFECTION

- Positive testing by RT-PCR assay (any source);
- Irrespective of clinical signs and symptoms.

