8.5.2.2 Immunogenicity

Post-baseline antibody titers from ELISA will be compared between treatment groups using ratios of geometric mean titers and associated 95% CIs.

Post-baseline seroconversion from ELISA will be compared between treatment groups using differences in proportions and associated Miettinen and Nurminen 95% CIs.

The summaries listed above will be stratified according to disease status of the subjects.

INO-4800	COVID19-311
Inovio Pharmaceuticals, Inc.	Clinical Protocol

Valid samples for statistical analysis purposes will be those collected within the days of the specified visit according to the Schedule of Events. Baseline is defined as the last measurement prior to the first treatment administration.

The PP population will be used for immunogenicity analyses.

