- i. On Day 0, cellular sampling requires 64 mL of whole blood (8 CPT tubes, each 8 mL of whole blood) prior to 1st dose. At all other time points, collect 32 mL of whole blood (4 CPT tubes, each 8 mL of whole blood). Cellular samples collected for all subjects at Day 0 pre-dose and Week 6; collected for approximately 10% of subjects at other indicated visits.
- j. On Day 0, humoral sampling requires a total of 17 mL of whole blood (two 10-mL red top serum collection tubes, each 8.5 mL of whole blood, to produce eight serum aliquots of 1 mL each). At all other time points, collect 8.5 mL of whole blood in a single 10-mL red top serum collection tube to produce four serum aliquots of 1 mL each.
- k. SARS-CoV-2 antibody.
- I. Saliva will be collected at study visits and bi-weekly at home between office visits. In-office collection time points for Screening, Day 0, Day 28, EOS and COVID-19 visits will be tested at the time of collection. All other stored saliva specimens will be selectively tested if a SARS-CoV-2 serology test becomes positive. The Day 0 and Day 28 RT-PCR results will not be required prior to dosing on that day.
- m. Nasal swab and saliva specimens.
- n. Subjects will be evaluated during a "COVID-19 assessment visit" when acute COVID-19 is suspected. The assessment visit may be performed in the clinic, subject's vehicle, or via telemedicine and should be completed within 3 days of symptom onset or within 3 days of a positive result of a SARS-CoV-2 test. Additional instructions for this visit will be provided in a separate study manual.
- o. For subjects with confirmed SARS-CoV-2 infection during the trial, a convalescent visit should be scheduled approximately 28 days after symptom onset, or in the absence of symptoms, the date of positive SARS-CoV-2 test. If acute symptoms are ongoing the site should follow up with the subject via phone call or unscheduled visit after symptom resolution or stabilization.
- p. Vital signs to be performed at COVID-19 assessment and convalescent visits include temperature, respiration rate, heart rate and oxygen saturation.

INO-4800	COVID19-311
Inovio Pharmaceuticals, Inc.	Clinical Protocol

1.0 **INTRODUCTION**

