 - Surgically sterile or has a partner who is sterile (i.e., vasectomy in males or tubal ligation, absence of ovaries and/or uterus in females). In the case of vasectomy, subjects should wait six (6) months post-vasectomy prior to enrolling;
 - Use of medically effective contraception with a failure rate of < 1% per year when used consistently and correctly from screening until 3 months following last dose. Acceptable methods include:
 - o hormonal contraception including implants, injections or oral;
 - two barrier methods, e.g., condom and cervical cap (with spermicide) or diaphragm (with spermicide);
 - o intrauterine device or intrauterine system;
 - abstinence when this is the subject's preferred and usual lifestyle. Note: Periodic abstinence (e.g., calendar, ovulation, symptothermal, or postovulation methods) and withdrawal are not acceptable methods of contraception.

4.2 **EXCLUSION CRITERIA**

- Acute febrile illness with temperature > 100.4°F (38.0°C) or acute onset of upper or lower respiratory tract symptoms (e.g., cough, shortness of breath, sore throat);
- b. Positive serologic or molecular (RT-PCR) test for SARS-CoV-2 at Screening;
- c. Pregnant or breastfeeding, or intending to become pregnant or intending to father children within the projected duration of the trial starting from the Screening visit until 3 months following the last dose;
- d. Positive serum pregnancy test during screening or positive urine pregnancy test immediately prior to dosing;
- e. Known history of uncontrolled HIV based on a CD4 count less than 200 cells/mm³ or a detectable viral load within the past 3 months;
- f. Is currently participating or has participated in a study with an investigational product within 30 days preceding Day 0 (documented receipt of placebo in a previous trial would be permissible for trial eligibility);
- g. Previous receipt of an investigational vaccine for prevention or treatment of COVID-19, MERS or SARS (documented receipt of placebo in previous trial would be permissible for trial eligibility).
- h. Medical conditions as follows:
 - Respiratory diseases (e.g., asthma, chronic obstructive pulmonary disease) requiring significant changes in therapy or hospitalization for worsening disease during the 6 weeks prior to enrollment;

INO-4800	COVID19-311
Inovio Pharmaceuticals, Inc.	Clinical Protocol

- History of hypersensitivity or severe allergic reaction (e.g., anaphylaxis, generalized urticarial or angioedema)

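### In v2.0 the per-protocol set removes only earlier symptomatic disease, so subjects silently positive at Day 0 or Day 28 stay in the primary efficacy analysis; the bias is small, and the repair is cheap

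*Protocol*

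**What the plan says.** Protocol v2.0, Section 8.4, makes PP the primary efficacy set. It requires all doses and no protocol violations, and has one rule on earlier illness: "Subjects with disease occurring prior to 14 days post-dose 2 will be excluded from the PP population". Section 3.7 separates two states. Disease (3.7.1) is "Positive testing by RT-PCR assay (any source) with any of the following COVID-19 related symptoms". Infection (3.7.2) is a positive RT-PCR "Irrespective of clinical signs and symptoms". Section 8.4 names only disease.

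Section 3.0 sets the question: "The primary objective of this trial is to evaluate the efficacy of INO-4800 in seronegative subjects". Other v2.0 provisions decide who reaches the analysis:

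- **Eligibility.** Section 4.2(b) excludes for "Positive serologic or molecular (RT-PCR) test for SARS-CoV-2 at Screening". Under Table 2, footnote a, Screening may be up to 30 days before Day 0.
- **Day 0 and Day 28 samples.** Serum for SARS-CoV-2 antibody and saliva for RT-PCR are taken before dosing at both visits (6.1.2.1), and this saliva is tested when collected (Table 2, footnote l). Section 6.4.9 adds: "The Day 0 and Day 28 RT-PCR results will not be required prior to dosing on that day".
- **Second dose.** Section 6.4.10 stops further dosing after a confirmed COVID-19 diagnosis. Infection without symptoms is not named.
- **Baseline.** For immunogenicity, Section 8.5.2.2 states: "Baseline is defined as the last measurement prior to the first treatment administration".

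The v1.0 PP set "includes all baseline seronegative subjects who receive all doses of Study Treatments and have no protocol violations"; v2.0 no longer carries that restriction. Section 8.1 of v2.0 says that the formal statistical analysis plan is what follows in Section 8, so in that version the definition is not deferred elsewhere.

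**The concern.** The population analysed is wider than the population in the objective. Taking baseline as the last value before the first dose, a subject who is antibody-positive at Day 0 is baseline seropositive, yet is analysed as part of the seronegative efficacy set.

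Such subjects could matter in two ways. They add person-time at reduced risk. Those with lingering RT-PCR positivity could also be counted after the window opens: as an infection or, with any one listed symptom, as a primary case that the vaccine had no chance to prevent. Both would pull estimated efficacy towards no effect.

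**Working it through.** **1. Trace one subject through v2.0.** Screening negative at Day −20; infected without symptoms; antibody- or PCR-positive at Day 0.
- Section 4.2(b): met, because it looks only at Screening.
- Section 6.4.9: dosing does not wait for the PCR result.
- Section 6.4.10: no COVID-19 diagnosis, so dose 2 is given.
- Section 8.4: both doses received, no stated rule broken, no earlier disease. The subject is in PP.

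A subject first PCR-positive without symptoms at Day 28 reaches the same end.

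**2. Reproduce the design figures** (Sections 8.5.1 and 8.6; follow-up ratio k = 1).
- Null p0 = 0.70/1.70 = 0.4118; alternative p1 = 0.40/1.40 = 0.2857; one-sided 0.025, exact binomial.
- With 160 cases, success needs at most 53 in the vaccine arm: exact alpha 0.0224, power 91.2%.
- N = 160 / (0.037 × (1 + 0.4)/2) = 6177.6, i.e. 6178.

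The stated figures hold, with 3.7% as the placebo rate. The point concerns the analysis set and not the sample size.

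**3. How many subjects?** The documents give no rate of silent early infection. Assumptions: 3.7% symptomatic over the 351 days from Day 42 to Day 393, constant hazard, placebo rate in both arms, and an asymptomatic share s of 50–80% (the range in v2.0, Section 1.2). Asymptomatic risk over 351 days = 0.037 × s/(1 − s): 3.7% at s = 0.5 and 14.8% at s = 0.8.

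| Interval | s = 0.5 | s = 0.8 |
|---|---|---|
| Day 0 to Day 42 (× 42/351) | 0.44%, about 27 | 1.77%, about 109 |
| Day −30 to Day 42 (× 72/351) | 0.76%, about 47 | 3.04%, about 188 |

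The second row is an upper figure, because it puts every Screening at the earliest permitted day.

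**4. Effect on primary VE (true value 60%).**
- Equal immune shares in the two arms: VE stays at 60%.
- Unequal shares: apparent VE = 1 − 0.4 × (1 − s_v)/(1 − s_p), where s_v and s_p are the immune shares in the vaccine and placebo arms. Take the largest placebo share, 3.04%. Of this, 0.148 × 30/351 = 1.26% arises before any dose and 1.77% after. If the vaccine prevented 60% of the later part from Day 0 onwards, s_v = 1.26% + 0.4 × 1.77% = 1.97%. Apparent VE = 1 − 0.4 × 0.9803/0.9696 = 59.6%, a shift of about 0.4 point.
- Carry-over cases: if a share f of the 160 cases predates any vaccine effect and splits 1:1, p = (1 − f) × 0.2857 + f × 0.5 and VE = (1 − 2p)/(1 − p).

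| f (assumed) | Cases | Apparent VE | Power |
|---|---|---|---|
| 2% | 3.2 | 59.2% | 89.1% |
| 5% | 8 | 57.9% | 85.3% |
| 10% | 16 | 55.7% | 77.4% |

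**5. Effect of excluding them.** Expected cases = 6178 × (1 − share removed) × 0.0259, where 0.0259 = 0.037 × 0.7.

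| Removed | Expected cases | Exact power |
|---|---|---|
| 1% | 158 | 90.1% |
| 2% | 156 | 88.9% |
| 3% | 155 | 89.9% |

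Power is not monotone because the exact test is discrete. The case loss is overstated if the removed subjects are partly immune.

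**The case against.** **Version.** v3.0 is the later protocol, and its Section 8.4 is not in the available text. Its summary of changes says the Phase 3 segment is largely unchanged, and its Section 3.0 still counts the 160 cases among seronegative subjects. That makes carry-over of the definition plausible but does not show it. This limit stands.

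**Dropped wording.** A reader might infer that v2.0 lost the seronegative restriction by mistake. The documents do not support that: v2.0 removed the seropositive cohort and added the Screening exclusion, so the qualifier looked redundant. What is left uncovered is the interval between Screening and Day 0. The v1.0 wording would not have excluded PCR positives at Day 28 either.

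**Infection endpoint.** A reader might infer that this endpoint is openly contaminated. Section 8.5.1 of v2.0 excludes subjects identified as cases that began before the window, and Section 8.5.2.1 analyses secondary incidence endpoints in the same manner. For the infection endpoint a case is any positive RT-PCR, so a PCR positive at Day 0 or Day 28 can be read as already excluded. This largely stands. What remains is antibody-only positives and the fact that the exclusion has to be inferred.

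**Adjudication.** A blinded committee reviews cases under a charter that is not shown, and it may discount old PCR positivity. The 5% and 10% carry-over rows are therefore illustrations; no document gives such a share.

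**Day 42.** One might extend the point to subjects positive at Day 42. v2.0 has no Day 42 visit: after Day 28 the next serology is at Day 56. Day 42 samples exist in v1.0 and v3.0 only.

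**Conclusion.** The gap is real in v2.0. Subjects silently antibody- or PCR-positive at Day 0, or PCR-positive at Day 28, remain in the primary PP analysis although the objective concerns seronegative subjects. Nothing else in the v2.0 text removes them from the primary analysis.

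Its size is modest. On the assumptions in the working, at most about 1–3% of subjects are involved, and the shift in primary VE from unequal immunity is about 0.5 point or less, towards no effect. A false claim of efficacy is not the risk. A larger loss would need carry-over cases of about 5% or more of the total, which the documents do not support. For the infection endpoint, the gain is mainly in handling antibody-only positives and in making an implied exclusion explicit. The change is worth making because it aligns the analysis set with the stated question at little cost, and not because the primary result is under threat.

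**What to change.** In Section 8.4, define PP as SARS-CoV-2 antibody-negative and RT-PCR-negative at Day 0, with no positive RT-PCR on samples already scheduled for testing before 14 days post-dose 2 (Day 28 and any illness visit). State that the same at-risk set applies to the infection endpoint. Confirm that Section 8.4 of v3.0 carries the same text. This concerns the analysis set only and implies no change to dosing.

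The Day 0 criterion uses pre-dose samples, so treatment cannot influence it. The Day 28 criterion comes after randomisation, as the existing disease rule does, so all subjects should stay in mITT and ITT.

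Any serology criterion after dosing must be nucleocapsid-based. v2.0 does not state the antigen of its antibody test, and a Spike assay would remove vaccine responders from one arm. Such a criterion is best kept as a sensitivity analysis where the samples exist (Day 42 in v3.0 only).

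Cost: wording, using samples already collected and saliva already tested; about 1–3% fewer PP subjects; roughly 155–158 expected cases and power of about 89–90%. Holding 160 expected cases instead would need N of about 6178/0.99 = 6241 to 6178/0.97 = 6370.
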